Rationale. As has been outlined in Section A of this proposal, there is no established noninvasive imaging or laboratory technique to identify neuroendocrine transdifferentiation in prostate cancer (NEPC). Our hypothesis is that interrogating the upregulation of the somatostatin receptor which occurs within a subset of prostate cancer patients, or prostate cancer metastatic lesions, is possible by utilizing ⁶⁸Ga-DOTATATE PET as a visual biomarker, which specifically binds to the somatostatin receptor SSTR2 (the somatostatin receptor most upregulated in NEPC) (36). To that end we will perform ⁶⁸Ga-DOTATATE PET imaging on up to 20 patients to determine the degree of uptake in patients with metastatic prostate cancer (mCRPC) who is about the start first line of treatment (abiraterone acetate or enzalutamide) for castration resistant disease. We believe that this inflection point best balances early detection of potential neuroendocrine transdifferentiation with imaging, as these patients typically have higher ECOG (Eastern Cooperative Oncology Group) performance status than those further along the continuum of their treatment. Patients with mCRPC will continue to receive standard of care therapy with no clinical decisions being made based upon the results of the ⁶⁸Ga-DOTATATE PET study. The goal of this study is not to compare the diagnostic performance of ⁶⁸Ga-DOTATATE in neuroendocrine tumors with other imaging modalities, as this has already been externally verified (39-41).

Our hypothesis is that patients with higher levels of ⁶⁸Ga-DOTATATE uptake on an initial PET scan (presumed NEPC) will have a shorter time to progression while on oral agents (abiraterone acetate or enzalutamide) due to inherent resistance to antiandrogen based therapeutics (42) when compared to those with lower ⁶⁸Ga-DOTATATE uptake.

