The patients will be also followed up in the context of this study (per clinical routine) for at least one-year post-therapy to determine if the degree of Ga-68 DOTATATE uptake correlates with progression free survival of disease as evidence by imaging progression, PSA progression, clinical progression, which defined by investigator and mortality (Objective 2). It is expected that higher Ga-68 DOTATATE uptake will lead to a shorter time to progression with discrete foci of uptake greater than liver being defined as positive for enhanced receptor expression, and thus indicative of malignancy.

C.1 Ga-68 DOTATATE radiolabeling

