Patients with metastatic prostate cancer who are failing standard androgen deprivation therapy and diagnosed with castration resistant disease will be the target recruitment demographic for scanning with Ga-68 DOTATATE. Following scanning with Ga-68 DOTATATE, patients will be treated according to standard of care per the clinician's discretion with oral agents (abiraterone acetate or enzalutamide) or other FDA approved agents. The results of the Ga-68 DOTATATE PET/CT will not influence the clinician's treatment decisions.

C.4 Routine Laboratory and Imaging Biomarkers

As per clinical routine, all patients will undergo routine imaging including CT, MR, FDG/PET/CT or bone scan and PSA evaluation within 90 days prior to the Ga-68 DOTATATE PET-CT study. Subsequent routine imaging and standard laboratory analysis (e.g. PSA level) will be performed according to the clinician's discretion. This is considered a clinical standard and will not be funded from the project budget. These studies will be performed with the standard Emory protocols on file.

C.5 Image Analysis of Ga-68 DOTATATE PET-CT

Methods: The methods of image analysis to be used for the Ga-68 DOTATATE PET-CT are as follows:

- 1) Images will be reconstructed with iterative technique and hardware fused (PET to CT) on a MimVista or similar workstation which enables SUV (mean, maximum) and total lesion activity as well as standard bi-dimensional size measurements of lesions. Whenever possible we will use 3 dimensional PET-Edge conformal regions of interest (ROI) to encompass the entire structure under question such as a lymph node or prostatectomy bed.
- 2) Visual inspection of the PET-CT images in separate sessions by a board certified nuclear medicine physician/nuclear radiologist. Up to 5 representative index lesions in each category will be selected as markers of Ga-68 DOTATATE uptake. If 5 lesions each are not definable in each patient, all demonstrable lesions up to 5 will be utilized. Lesions chosen will be independent but may coincide with index lesions on conventional imaging.
- 3) Ga-68 DOTATATE organ and tumor uptake will be quantified using maximum standardized uptake values (SUVmax) and mean standardized uptake values (SUVmean). SUVmax of pathological findings will be compared with accumulation of the radiotracer in a liver as a reference organ. Definitive criteria defining high, moderate, and mild uptake have not been

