established. However, based on literature examples (30), a diagnosis of high Ga-68 DOTATATE uptake will be assigned to lesions with a SUVmax ≥ 8 , moderate Ga-68 DOTATATE uptake will be assigned to lesions with a SUVmax ≥ 5 , and mild Ga-68 DOTATATE uptake will be assigned to lesions with uptake greater than liver and/or SUVmax ≥ 3 .

- 4) In addition, the measurements above will be supplemented by the following from RECIST 1.1 Criteria (44).

C.6 Comparison to Ga-68 DOTATATE uptake with standard response criteria

For response criteria to oral agents, patients will serve as their own controls.

- 1) Ga-68 DOTATATE PET-CT uptake will be correlated with clinical response criteria including time to PSA progression, which is defined as the time from initiation of treatment to the date of earliest objective evidence of PSA progression, which will be assessed at each clinic visit, and is defined as time from initiation of treatment to the date of PSA absolute increase ≥ 2 ng/mL and $\geq 25\%$ above nadir or baseline values confirmed by a second consecutive value obtained at least 3 weeks later or death due to any cause. Repeat imaging during treatment will obtain per clinician discretion such as when any sign of clinical progression or PSA progression. Radiological progression of bone lesions will be determined by using Prostate Cancer Working Group 3 (PCWG3) recommendations for clinical trial conduct in castration resistant disease and radiographic progression of soft tissue lesions will be determined by using modified RECIST 1.1 criteria.

We will utilize 6 and 12 month progression free survival outcomes and patients will be consented to be followed until there is any evidence of progression.

C.7 Follow up

This will be done as part of routine standard of care without special visits required of the patient. Clinical visits will be determined by clinician's discretion as will be ordering of laboratory tests including CBC, CMP, testosterone and PSA. Within one year after Ga-68 DOTATATE PET-CT imaging (or earlier if progression), imaging response to therapy using standard criteria including repeat CT or MR, bone scan and PSA will be obtained. Accrual goals will be 4 patients every year for a total of 20 patients in 5 years.

D. Patient selection

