Patients will be recruited from the Genitourinary Medical Oncology clinic at Winship Cancer Institute per the inclusion and exclusion criteria below. It is estimated that a minimum of 20 patients per month who meet inclusion criteria are seen in the Genitourinary Medical Oncology clinic at Winship Cancer Institute. However, if we do not enroll our target goals, patients with mCRPC from Georgia Cancer Center for Excellence at Grady will be referred to this study as [name] also staffs that genitourinary oncology clinic.

Inclusion Criteria:

- 1) Patients must be 18 years of age or older.
- 2) Patients with metastatic castration resistant prostate carcinoma with skeletal, visceral and/or nodal involvement.
- 3) Ability to lie still for PET scanning

- 4) Patients must be able to provide written informed consent

Written consent will be obtained from the patient prior to the PET scan day and documented. Eligibility checklist will be verified with the patient prior to the scan day once consent is obtained.

Procedures:

PET Scan Day

- Obtain written informed consent if not earlier obtained.
- Inclusion/exclusion criteria review if not earlier done.
- Medical history and medication review if not earlier done.

E. Statistical Analysis

Patient baseline characteristics and degree of ⁶⁸Ga-DOTATATE uptake will be summarized using descriptive statistics. The inter-rater agreement will be assessed by Kappa statistics or intra-class correlation coefficient. The degree of uptake will be plotted against length of time to progress, and the association will be described by Spearman correlation coefficient with 95% confidence interval (CI). In addition, we will dichotomize degree of uptake by median and define it as high vs. low, and apply Wilcoxon rank sum test or Fisher exact test wherever appropriate. The association with progression free survival will be able to describe by Kaplan-Meier method along log-rank p-value (due to the small sample size, this may not be feasible). This is a pilot study with main goal to evaluate the feasibility, and no statistical power is possible.

F. Adverse Events

An adverse event is defined as any untoward medical occurrence associated with the use of a drug in humans whether or not considered drug-related.

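### Nothing in the plan masks the DOTATATE result from those who call and date progression, so investigator-defined clinical progression could be called earlier in high-uptake patients, in the direction of the hypothesis

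*Combined protocol and SAP*

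**What the plan says.** **Endpoint.** The Objective 2 paragraph of Section C (Experimental design) correlates uptake with progression-free survival, judged by "imaging progression, PSA progression, clinical progression, which defined by investigator and mortality (Objective 2"). No criteria for the clinical component appear anywhere. C.6 gives rules for the other components: a confirmed numerical PSA rise, PCWG3 for bone and modified RECIST 1.1 for soft tissue.

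**Timing of assessment.** C.6: "Repeat imaging during treatment will obtain per clinician discretion such as when any sign of clinical progression or PSA progression". C.7: "Clinical visits will be determined by clinician's discretion as will be ordering of laboratory tests including CBC, CMP, testosterone and PSA". The only calendar anchor is in C.7: "Within one year after Ga-68 DOTATATE PET-CT imaging (or earlier if progression), imaging response to therapy using standard criteria", to be obtained by repeat CT or MR, bone scan and PSA.

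**Use of the PET result.** The Rationale in Section B promises "no clinical decisions being made based upon the results of the" PET study. C.3 says: "The results of the Ga-68 DOTATATE PET/CT will not influence the clinician's treatment decisions". C.5 describes the PET read as "Visual inspection of the PET-CT images in separate sessions by a board certified nuclear medicine physician/nuclear radiologist".

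**Expectation.** Section B labels high uptake as presumed neuroendocrine disease, and Sections B and C both expect it to shorten time to progression.

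**Analysis.** Section E names a Spearman coefficient with 95% CI first, then a median split with Wilcoxon or Fisher tests, then Kaplan-Meier and log-rank if feasible. It states that no power can be given.

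**The concern.** The predictor is fixed before follow-up starts, and one component of the outcome is a judgement. If the person making that judgement knows the scan result, and the protocol has told them what a high-uptake scan should mean, progression may be declared earlier in high-uptake men without any difference in disease. The distortion would run in the hypothesised direction. It would enter the 6- and 12-month PFS, the Spearman coefficient and any log-rank comparison.

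The opening summary says that the results may be used to design larger studies, so an inflated association could be carried forward. Masking also cannot be restored once a result has been seen.

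**Working it through.** The plan states no effect size, error rate or expected progression time, so there is no figure to reproduce. The check has two parts.

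**1. Reading the safeguards against the endpoint**

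| Question | Section B, Rationale | C.3 | C.5 |
|---|---|---|---|
| Does it limit use of the result in care? | Yes, all clinical decisions | Yes, treatment decisions | Not addressed |
| Does it say who may see the result? | No | No | No |
| Does it cover declaring or dating progression? | No | No | No; it concerns the PET read |

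No masked or central review of progression is described elsewhere. By component:
- Death is protected.
- The PSA threshold is numerical and confirmed, although its date depends on when PSA is drawn.
- Radiology follows published criteria, although its date depends on when scans are ordered.
- Clinical progression has neither protection.

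**2. Illustrative size with no true association**

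From the documents: 20 patients and a median split, hence 10 v 10.

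Assumed, not in the documents: exponential progression with median 9 months; detection at 3-monthly scans with a random offset in both groups; log-rank at 18 months; no separate PSA detection; subjective over-calls in the high-uptake group only.

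*Six-month PFS without over-calling.*
- Hazard: λ = ln 2 / 9 = 0.0770 per month.
- True PFS: S(3) = 0.794 and S(6) = 0.630.
- Observed PFS, averaged over the scan offset: (S(3) − S(6)) / (3λ) = 0.164 / 0.231 = 0.71.

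*With 15% over-called by 6 months.* PFS is 0.71 × 0.85 = 0.60 in the high-uptake group, a gap of about 11 points, or roughly one patient in ten.

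*With 5% over-called by 6 months.* PFS is 0.71 × 0.95 = 0.67, a gap of about 4 points.

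*What happens after 6 months matters.* A hazard giving 15% by 6 months, if it never stops, implies 1 − 0.85² = 28% by 12 months and 1 − 0.85³ = 39% by 18 months, absent other events.

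Simulated log-rank rejections in the hypothesised direction:

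| Over-calling in high-uptake patients | Rejections |
|---|---|
| None | about 3% |
| 15% by 6 months, then stops | about 6-7% |
| 15% by 6 months, continuing to 18 months | about 11% |
| 5% by 6 months | about 4% |

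In the two 15% cases the mean Spearman rho is about −0.09 to −0.14, where the truth is 0.

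*A different mechanism as a cross-check* (medians 9 to 16 months, all patients followed to an event):
- All high-uptake patients called 3 months early: mean rho −0.08 to −0.13, log-rank rejections 6-10%, 6-month PFS lower by about 9-13 points.
- Half of them called 2-3 months early: mean rho −0.03 to −0.06, rejections 4-5%.

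*Against sampling noise.* With n = 20, the 95% interval around rho = 0 is ± tanh(1.96/√17) = ±0.44. All these shifts lie well inside it.

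**The case against.** The strongest reply is that the Section B promise covers all clinical decisions, and ordering a scan is one. Extra imaging prompted by the PET would then breach the protocol. That stands, so the size above rests on subjective calls alone. A reader might go further and suppose that high-uptake men would be scanned every 3 months and others every 6. By itself that gives about 5% rejections and a 9-point gap in 6-month PFS. Added to continuing over-calling, it gives about 18-19%. These figures assume the breach and leave out PSA. If 70% of progressions also showed on equal 6-weekly PSA checks (again an assumption), the imaging-only gap would fall to about 3 points and rejections to 3.5%.

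A reader might also infer that clinicians will be given the PET result. The documents do not say so; they are silent. The gap is the absence of a rule, not evidence of release.

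Nor does the Section D remark that someone "also staffs that genitourinary oncology clinic" show that study staff judge their own patients. It refers to a back-up referral site, used only if accrual falls short, and the person's role cannot be seen.

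Finally, this is a secondary objective in a 20-patient feasibility study, Section E doubts that a log-rank test will be feasible, and mild bias would be lost in noise. That limits the weight of the point. It does not remove it, because the promise about clinical decisions names no mechanism and does not reach the declaring or dating of progression.

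**Conclusion.** The point holds as a gap in ascertainment. Clinical progression is subjective and undefined, no text masks whoever calls it, and any bias would favour the hypothesis. It applies mainly to clinical-only events, and to a lesser degree to the dates of PSA and imaging events.

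Under the stated assumptions the effect is modest to moderate: up to about 11 points on 6-month PFS, false positives of about 4-11% against about 3%, and a mean rho shift of about −0.09 to −0.14 at the 15% rate. The over-call rate, its duration and the median are all assumed, and PSA detection is not modelled, so these are illustrations and not forecasts. The feasibility objective is unaffected. This is an inexpensive improvement worth making before more results are read, not a fatal flaw.

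**What to change.** 1. **C.3/C.5.** State that the DOTATATE read (SUVs, grade, positive or negative) is held by the imaging team. It is not released to the treating oncologist, or to whoever dates progression, until that patient's progression date is recorded or follow-up for the analysis ends. Release at 12 months would be too early: patients are followed until progression, and the Spearman analysis uses later dates. Provide a release route for safety-relevant findings, with each release logged and the patient flagged.
2. **C.6/Section E.** Record which component each progression event rests on, and the date of and reason for each follow-up scan. Report PFS and the Spearman analysis with and without events resting only on investigator-defined clinical progression. Repeat both without patients whose result was released early.

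**Cost.** A few sentences and restricted access to one research report, with no added procedure. Withholding the read fits the existing commitment not to act on it. Masking will be imperfect for patients with early release. The analysis without clinical-only events will have fewer events. Because C.6 follows patients until any evidence of progression, Section E should also say whether those patients are censored at the clinical call or followed on through routine data.

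### Nothing keeps the DOTATATE result from whoever judges and dates progression, or locks the uptake reads before outcomes are known, so the secondary association could be biased toward the hypothesis

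*Combined protocol and SAP*

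**What the plan says.** **Endpoint.** Section C, Experimental design, bases progression-free survival on imaging progression, PSA progression and "clinical progression, which defined by investigator and mortality". Section C.6 gives criteria for three components: a numeric, confirmed PSA rise, PCWG3 for bone and modified RECIST 1.1 for soft tissue. No section gives criteria for clinical progression.

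**Timing of assessments.**
- C.4: "Subsequent routine imaging and standard laboratory analysis (e.g. PSA level) will be performed according to the clinician's discretion".
- C.6: "Repeat imaging during treatment will obtain per clinician discretion such as when any sign of clinical progression or PSA progression".
- C.7: "Clinical visits will be determined by clinician's discretion as will be ordering of laboratory tests including CBC, CMP, testosterone and PSA".
- The one anchored assessment is also in C.7: "Within one year after Ga-68 DOTATATE PET-CT imaging (or earlier if progression), imaging response to therapy using standard criteria".

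**Use of the PET result.** C.3 says "The results of the Ga-68 DOTATATE PET/CT will not influence the clinician's treatment decisions". The Rationale in Section B is wider and says that no clinical decisions will rest on the PET. Neither says who receives the result.

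**PET reading.** C.5 calls for "Visual inspection of the PET-CT images in separate sessions" and lets the reader choose up to five representative index lesions per category. It acknowledges that definitive uptake criteria do not yet exist. Section E plans inter-rater agreement. Nothing says when the reads become final relative to outcome.

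**Expected direction.** The Rationale in Section B and the Experimental design both state that higher uptake should go with shorter time to progression.

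**The concern.** The secondary objective relates an exposure (uptake) to an event time. Three features together leave that relation open to ascertainment bias: a component that depends on judgement, dates that depend on when someone chooses to look, and a declared expectation about which patients will fail early. If the person judging progression knows the uptake, an equivocal clinical picture may be called progression sooner in a high-uptake patient. Earlier visits or tests would also bring forward the PSA and imaging dates, even though those components have firm criteria.

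There is a smaller route in the other direction. Accrual is planned over five years. If index lesions are selected or uptake is categorised after a patient's course is known, the exposure could be shaped by the outcome.

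The stake is the preliminary estimate. The opening summary says the results may be used to design larger studies, and Section B gives an early predictive imaging biomarker as the ultimate goal. A correlation partly produced by ascertainment would be carried into that work.

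**Working it through.** The plan states no power, effect size or event count, so there is no statistical figure to reproduce. The accrual goal is consistent: 4 per year × 5 years = 20.

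**1. What the safeguards cover**

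| Step | Covered by the text? |
|---|---|
| Choice of treatment | Yes (C.3) |
| Clinical decisions, which can be read to include ordering a scan | Yes, as a statement of intent (Section B, Rationale) |
| Judging clinical progression | Not addressed |
| Assigning the progression date | Not addressed |
| Reading follow-up bone scan and CT/MR without the PET result | Not addressed |
| Finalising uptake reads before outcome is known | Not addressed |

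**2. How large the bias could be**

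From the plan: N = 20, a median split (about 10 vs 10), Spearman correlation, and a possible log-rank test. Assumed, because the documents give no values: exponential time to progression with median 12 months (rate λ = ln 2 / 12 = 0.0578 per month), no true association with uptake, two-sided 5% tests, censoring at 24 months for the log-rank test, fully observed times for Spearman, and the ascertainment differences below. Each scenario used 10,000 simulated trials. The Monte Carlo standard error near 5% is √(0.05 × 0.95 / 10,000) = 0.2 percentage points.

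*Route A, earlier looking.* Observed time = true time + delay, where the delay is uniform on (0, k) and k is the interval between looks.

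*Route B, earlier calling.* A fraction f of high-uptake patients is called at half the true time.

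| Scenario (high vs low uptake) | Mean rho | False positives, Spearman | False positives, log-rank |
|---|---|---|---|
| No difference | 0.00 | 5.3% | 5.5% |
| A: k = 2 vs 4 months | −0.04 | 5.4% | 5.7% |
| A: k = 2 vs 6 months | −0.08 | 6.7% | 7.3% |
| A: k = 3 vs 12 months | −0.16 | 10.6% | 11.0% |
| B: f = 30% | −0.07 | 6.0% | 7.9% |
| B: f = 50% | −0.13 | 8.8% | 11.2% |
| B: f = 100% | −0.25 | 18.5% | 29.9% |

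Two rows can be checked by hand on the proportion progressed by 12 months:
- Route A: 1 − 0.5 × (e^(λk) − 1)/(λk). For k = 3, λk = 0.173, giving 1 − 0.5 × 1.092 = 0.45. For k = 12, λk = 0.693, giving 1 − 0.5 × 1.443 = 0.28. The simulation gave 45% and 28%.
- Route B, f = 50%: 0.5 × 0.75 + 0.5 × 0.50 = 0.625, against 0.50 in the low group. The simulation gave 63% and 50%.

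With assumed medians of 9, 12 and 18 months, mean rho ranged from −0.03 to −0.25 and was always in the hypothesised direction.

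**3. A second lag model**

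With exponential detection lags, an assumed median of 10 months and N = 20, mean lags of 1 vs 2, 1 vs 3 and 1 vs 4 months gave false-positive rates of about 5.5%, 7.2% and 7.8% (Spearman) and 6.3%, 8.3% and 8.7% (log-rank). Both models put mild differences at about 5 to 9%.

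**The case against.** **Some of the opposing case stands.** The Rationale's bar on clinical decisions is wider than C.3 and can be read to include ordering a scan. The example triggers in C.6 are signs of clinical or PSA progression, and uptake is not among them. Most components are criterion-based or are death. Uptake is quantified by SUV on a baseline scan, with inter-rater agreement planned, so the reader-side route is the weaker one. All of this concerns the secondary objective of a pilot that disclaims power.

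**What it does not answer.** The bar is a statement of intent with no mechanism. It does not reach the judgement or dating of progression, and separate reading sessions do not mean reads made without knowledge of outcome.

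**Stronger readings a reader might infer, and why they fail.**
- *The investigators see the uptake result.* The documents do not say who receives the report. The supportable statement is that no withholding is described.
- *The protocol promises only that treatment is unaffected.* The Rationale goes further, as above.
- *High-uptake patients will be scanned and called earlier, and the bias cannot be separated from a real effect.* This could happen; nothing shows that it will. The criterion-based components allow partial separation.
- *The bias is large.* The 1 vs 2, 3 and 4 month lags give hazard ratios of roughly 1.1, 1.2 and 1.3 in very large simulated samples. Section E plans no Cox model, and with 20 patients the same lags raise false positives only to about 5 to 9%.

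**Conclusion.** The concern holds as a gap in safeguards; it does not show that bias will occur. Clinical progression has no criteria, assessment timing is discretionary, the expected direction is declared, and no section masks the progression call to uptake or locks the uptake reads.

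Any resulting bias would favour the hypothesis. Its size depends wholly on assumed differences in ascertainment. Under mild differences it is small (mean rho about −0.04 to −0.08 in Route A). Under strong ones it is material: mean rho −0.16 with looks every 3 vs 12 months, and −0.25 if every high-uptake patient is called at half the true time. The last is an extreme case.

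The feasibility objective is not affected. This is a cheap improvement worth making before the secondary analysis.

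**What to change.** 1. State that index-lesion selection, SUV values and uptake category are finalised and locked before outcome data are linked.
2. Have a study team member assign the progression date from PSA values, PCWG3/RECIST imaging reports and chart data, without the DOTATATE read. The documents do not name anyone who already does this, so the role must be assigned.
3. Report the uptake–progression association a second time with PSA progression, radiographic progression and death only, leaving out investigator-defined clinical progression, and set it beside the full composite. PSA belongs in this set because C.6 defines it numerically with confirmation.
4. State who receives the DOTATATE report, tabulate assessment dates by uptake group, and record discretionary scan timing as a limitation.

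**Cost.** Protocol wording, the order of data handling, some time from the team member who dates progression, and one extra analysis. There are no added procedures and no change to care. Masking is only partial if treating clinicians see the report, and assigning dates afterwards without the PET read cannot undo a scan that was ordered early. Item 4 makes that remaining problem visible but does not remove it.
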